We will take several steps to insure that staff follows procedures to maintain privacy and confidentiality. First, all new staff will be required to be oriented and trained in procedures to maintain confidentiality of information, including written and electronic materials. Staff is required to sign a Confidentiality Contract, which describes the serious nature of maintaining confidentiality and enumerates procedures for maintaining it. All project staff will be required to take and pass the CITI training course on the protection of human subjects. In addition, project staff will be instructed about PHI, the need to identify individuals by arbitrary identification numbers, the need to file materials with names or key lists separate from research materials, electronic privacy, the need for non-identifiable correspondence materials from the Center, removing or blacking out participant names from any forms; sorting all data in locked file cabinets; securing all computers that store data; and destroying audiotapes used for interviewer reliability checks and fidelity ratings at the end of the project.

16. Final Product(s)

Final results will be reported in aggregate form only. Results may be prepared for publication in peer reviewed professional journals in mental health and rehabilitation, and used as preliminary data for future development of the intervention.

17. Financial Summary

The project is being funded by the National Institute of Mental Health - Grant Proposal MH102230-01A1.

18. Compensation for Injuries

We do not anticipate any injuries related to participation in the study and do not plan on any compensation for injury. There may be a minimal risk for physical injuries while individuals are taking pictures in the community. The Informed Consent Form informs participants that if this occurs, the cost of required medical services will have to be covered by their insurance or by them personally.

19. Insurance

There are no entitlements or insurance for the subject that will be purchased or invoked for this project. There is no other insurance purchased by Boston University for the subjects.

20. Use of DMH Resources

No DMH resources will be used for this study.

21. Other IRBs Involved

Boston University Charles River Campus (CRC) IRB.

22. Adverse Events

An adverse event for this study is consonant with the guidelines set forth by the MA DMH. Reporting guidelines will be followed in the event of an adverse event.

It is highly unlikely that we will experience a serious, unexpected adverse events related to study participation in the Photovoice intervention. Riverside staff will be asked to report any unexpected serious adverse event among study participants to the PI within 3 days of becoming aware of the occurrence of any such event. The Project Coordinator will be required to report such events to the PI within 24 hours of becoming aware of their occurrence. The PI will follow the requirements of the Data Safety and Monitoring Board and the MA DMH IRB (the IRB of record for the study): a) in case of a serious adverse event – verbal notification as soon as possible and in writing by the next business day following the event; and b) non-serious adverse event will be monitored, recorded, and reported to the IRB Chair every 4 months. The PI will notify NIMH within 7 days of becoming aware of the occurrence of a study-related serious adverse event and will report non-serious adverse events in the corresponding progress reports to NIMH.

Continuous and close monitoring of study participants' safety by the PI will occur in conjunction with the Dartmouth College Data Safety Monitoring Board (DSMB). The current research project is a Phase II trial, involves a low risk intervention, is not conducted with a vulnerable population, and is not blinded to participant or treatment provider. However, given that the research is being conducted in three locations within one agency, a Data Safety and Monitoring Board (DSMB) will be constituted to provide additional human subjects' oversight. Two Investigators on this project are faculty at Dartmouth Medical School: Drs. [name] and [name] (statistician). Through this affiliation with Dartmouth, we plan to use their standing DSMB comprised of three psychiatrists and a psychologist (see attached bio sketches of the Dartmouth Medical School DSMB members). [name] has used the Dartmouth DSMB for multiple prior RCTs, supported by NIMH, evaluating the impact of psychosocial interventions on persons with SMI. The DSMB will establish a risk level for the study, and based on that assessment

will determine the frequency of DSMB meetings and review of pertinent data. The DSMB Chair ([name]) will be notified by the PI of serious adverse events that are study related using the protocol specified in the next paragraph. An ongoing record of all adverse events will be kept by the PI for use and review of the DSMB at the meetings. Minutes will be kept of DSMB meetings, including any discussion or decisions made about adverse events, and including those that could affect the conduct of the study. The DSMB will report back to the PI within one business day any implications for patient safety that arise from discussions during the scheduled DSMB meetings.

23. Required Attachments

Resume of the Principal Investigator
Certificate of Completion of the Human Subjects Training Course
Unaffiliated Investigator Agreement
Recruitment Flyer and
Consent to Contact Form
Informed Consent Form
Copies of the research instruments
Competency quiz

24. Attachments that are appropriate, when applicable:

- (a) Approval Form(s) from other IRBs that have reviewed this project.
- (b) Copies of non-standardized questionnaires, instruments, tests, etc.
- (c) Copies of posters, flyers, letters, etc.
- (d) Scripts of intended communications by telephone or interview.
- (e) External research protocols (usually, only five (5) copies are required of the technical drug research protocols - check with the CORRC before submitting materials).

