When a referral using the Consent to Contact form is made to the project, the potential participant will be contacted by phone or in person by the Project Coordinator to further determine their understanding of the research and their interest in participation. Prior to the phone call the Project Coordinator will obtain information about the person's diagnoses, including history or diagnosis of intellectual disability. In case an interested individual has a diagnosis associated with intellectual disability, the Project Coordinator will contact this person and inform him/her that they don't meet the study eligibility criteria based on information in their chart record. The Project Coordinator will explain the following to interested individuals who meet diagnostic eligibility: the details of the study, random assignment to two conditions, the interventions, and the research interviews as well as provisions for maintaining privacy and confidentiality. The Project Coordinator will screen for inclusion and exclusion criteria during this initial contact. Thus, all screening will be completed prior to administration of informed consent without implications for participants' compensation; hence, no references to pre-consent screening are included in the ICF. If the person remains interested in the study, the Project Coordinator will set up an appointment for the informed consent. If a person has a legal guardian, the guardian will be involved in the consent process. For those individuals who do not have a guardian, the Project Coordinator will explain the study in person and ask a brief set of questions to determine whether the individual has understood the nature of the research project, including the assessments and treatment approaches. We will provide corrective information as needed if the individual is unable to answer the quiz questions during the consent process, followed by additional checking to assure a participant's full and knowing consent. Potential participants who continue to express interest in the study and are able to demonstrate their understanding of the study by correctly answering these questions will then be asked to sign the informed consent form. Individuals who meet the eligibility criteria and who are able to provide full and knowing consent will proceed to scheduling of the baseline assessment with the Clinical Interviewer. Upon completion of the baseline assessment, participants will be randomly assigned to either the experimental (Photovoice) or the enhanced Services as Usual (SAU) conditions. The Project Coordinator will contact each participant and explain their randomization condition. Participants randomized to participate in the Photovoice program will be informed about the date of their first Photovoice session and participants randomized to the control condition will be informed about the date of the 60-minute peer-led group discussion session about understanding and coping with prejudice and discrimination. The Clinical Interviewer will be blind to participants' randomization.

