A total of 192 individuals with SMI (50% with schizophrenia spectrum disorders) will be randomized to either the Photovoice program (plus usual services) or enhanced SAU. Participants will be assessed by the Clinical Interviewer at baseline, post-treatment, 3-month and 6-month follow-ups on a range of primary and secondary outcomes related to personal stigma, coping, and functioning. Primary analyses will test the hypotheses that the Photovoice program will lead to significantly greater reductions in self-stigma and perceived stigma, greater improvements in proactive coping with psychiatric prejudice and discrimination, and greater improvements in community functioning and integration than SAU. Secondary analyses will evaluate whether the Photovoice program leads to greater gains than SAU in psychological adjustment, including wellbeing, personal growth and recovery.

Outcome measures include demographics, diagnosis, symptoms, levels of self-stigma and perceived stigma, coping with stigma, psychosocial functioning, community integration, psychological wellbeing, and recovery. All assessment interviews will be conducted in individual, face-to-face meetings with study participants in private offices at the research sites. Psychiatric diagnoses will be determined at baseline with the MINI. Eligibility determination will be supplemented by chart review of psychiatric diagnoses and presence of intellectual disability. All other primary (personal stigma, community functioning and integration) and secondary (psychological wellbeing, personal growth and recovery) outcome measures will be evaluated at baseline, post-treatment, 3-

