month and 6-month post-treatment follow-ups by the Clinical Interviewer who will be blind to the participant randomization status. The Clinical Interviewer will be trained in methods for eliciting self-report information, and standard interviewing procedures. In order to ensure high reliability and prevent rater drift of the Clinical Interviewer, we will audiotape all assessments and we will randomly select 10-15% for reliability checks. We will collect all relevant service utilization information from Riverside using their administrative databases after participants have completed the 6-month follow-up assessment. Eligible individuals who consent to participate at the study will complete a second Riverside Release of Information (ROI) form to authorize release of service utilization data since the first ROI will authorize only release of their chart diagnoses to determine eligibility.

We will be using the following measures to assess these outcomes:

Mini Neuropsychiatric Interview (MINI) - is a widely used 15-minute structured interview assessing the presence of 17 DSM-IV Axis I disorders with good concordance with the SCID and the CIDI and with acceptable test-retest reliability.

Brief Psychiatric Rating Scale - is a 24-item scale that rates severity of a variety of psychiatric psychotic symptoms, positive and negative symptoms on a 7-point scale of 1 (absent) to 7 (severe).

Approaches to Coping with Stigma - (Link et al., 1989) – is a 27-item, 4-point scale (strongly disagree to strongly agree) measuring strategies to cope with stigma: secrecy, withdrawal, distancing, educating others, and challenging others. The total score of the first three subscales will represent the index for Avoidant Coping and the total score of the last two subscales – the index for Proactive Coping with Stigma. Internal consistency for subscales range: .63-.84.

Internalized Stigma of Mental Illness Scale - a 29-item, 4-point scale (strongly disagree to strongly agree) assesses behaviors, thoughts and feelings that are self-stigmatizing and includes alienation, stereotype endorsement, discriminatory experiences, social withdrawal, and stigma resistance subscales. Internal consistency is .9 and test-retest reliability is .92.

The Stigma Scale (King et al, 2007) - is a 28 item, 5 point scale (strongly disagree to strongly agree) measuring experienced and anticipated stigma. Internal consistency ranges from .85-.87 and test-retest reliability from .4 to .7.

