Heinrich's Quality of Life Scale-Client Version - Is a 21 item semi-structured interview based rating of individual's psycho-social functioning and satisfaction with various life domains.

Temple University Community Participation Scale - is a 26 item instrument measuring frequency of participation and importance of various community activities (e.g., movies, library). Test-retest reliability is .7 and internal consistency is .9.

Scales of Psychological Well-Being - is a 54-item measure rating wellbeing (from strongly disagree to strongly agree) including subscales of mastery, personal growth, purpose in life, self-acceptance, autonomy and positive relations with others. Internal consistency is .94. It has been successfully used with individuals with SMI.

Maryland Assessment of Recovery - is a 25-item scale that assesses a person's sense of recovery from mental illness across a variety of dimensions. Internal consistency is .95 and test-retest reliability is .89).

Personal Growth and Recovery Scale - (BU CPR, 2009) - is a 16-item, 4 point scale (strongly disagree to strongly agree) developed for previous Photovoice study. Items tap aspects of person's psychosocial functioning and recovery. Internal consistency is 0.94 and retest reliability is .79.

Photovoice Program Fidelity Scale - the Photovoice Fidelity Scale was developed and used in our pilot RCT study (Russinova et al., 2014). The scale includes content fidelity items specific to each of the 10 Photovoice sessions and 13 process fidelity items which are specific to the Photovoice program as a whole. All items are measured on a 4-point scale from 1, "strongly disagree" to 4, "strongly agree". All Photovoice sessions will be audiotaped and fidelity will be assessed based on review of all audio-recorded sessions.

We will use a **Demographic Questionnaire** developed by the Boston University Center for Psychiatric Rehabilitation and previously used in multiple research studies. Questions inquire about the person's demographic characteristics, such as age, race, gender, education, employment status, housing situation, and basic clinical characteristics, such as perceived physical health and use of different mental health services in the past 3 months. We are using an abbreviated version of this questionnaire at post-treatment and follow-up assessments to capture information only on time varying variables included in the questionnaire.

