Interviewer will initiate a phone call with each study participant approximately two weeks before the due date of each assessment and will schedule an appointment to administer the assessment. If the participant is not available, the Clinical Interviewer will leave a message asking the participant to call back to schedule an assessment. If the participant does not respond within two days, the Clinical Interviewer will make another call using the same procedural approach. If the participant still does not respond within two days, the Clinical Interviewer will send an email if such is available and will follow up depending on the participant's response. At the same time, the Clinical Interviewer will contact Riverside staff involved in the study to inquire about the participant's whereabouts in case information about changes in the participant's programmatic status (i.e., hospitalization, expulsion, etc.) has not been already provided to the research staff. Participants agreement to have Riverside staff provide information about their thereabout will sought as part of the initial consenting for study participation. In addition, we will send a letter to the participant's known address with information about the relevant study assessment point. If the participant does not respond to the email and letter and there are no changes in their programmatic status, the Clinical Interviewer will call the contacts identified by the study participant on the Locator Form they completed at the baseline assessment and will ask about ways to contact the participant either directly via new phone number or email or indirectly with the help of the contact person. If all these efforts to reach the participant are not successful, they will be repeated for the next assessment point.

The data will be managed by project staff, using the same procedures we have used for longitudinal studies and randomized trials conducted by the Center. We will design systems for tracking specifically for this project using Microsoft Access.

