We believe that there are minimal risks resulting from participation in this study. The study design does not require that the individual's current mental health services be disrupted or altered in any way. Furthermore, anecdotal information from piloting the photovoice program suggests that it is a meaningful and engaging intervention and one that resonates well with participants. We have had no indications of distress or concern on the part of participants who participated in the several pilot sessions of the Photovoice. However, should an individual become distressed during a session, there are several steps we will take to minimize and address problems. First, all sessions are being conducted by highly skilled and experienced peer specialists, including one co-leader who is a certified peer specialist. These individuals have been trained and supervised at the Boston University Center for Psychiatric Rehabilitation to deliver similar interventions so that they will be experienced in detecting signs of distress. Peer specialists from Riverside who will be trained as Photovoice co-leaders will receive additional training about detecting and addressing signs of distress during the delivery of the Photovoice sessions. All Photovoice peer co-leaders will receive ongoing supervision during the course of the proposed research as well to insure that they are handling any issues that arise during the study with skill and sensitivity. If a participant becomes distressed during a class, one of the co-leaders will attend to the person to determine if their distress can be alleviated within the class. If that is not possible, they will be brought out of the group setting and attended to privately. If the co-leader is unable to address the person's distress, clubhouse staff will be notified to intervene, and if necessary, the individual's clinician or case worker will be contacted for further assistance.

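### The blinded Clinical Interviewer also makes the tracing contact with study-involved agency staff, a step that can incidentally reveal the arm

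*Protocol*

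**What the plan says.** **Blinding.** The recruitment and consent text before Section 7 of the protocol states: "The Clinical Interviewer will be blind to participants' randomization". Section 7 repeats it, with outcomes evaluated "by the Clinical Interviewer who will be blind to the participant randomization status". One role covers every visit: "Participants will be assessed by the Clinical Interviewer at baseline, post-treatment, 3-month and 6-month follow-ups".

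**Tracing.** The contact procedure in Section 7 starts about two weeks before an assessment is due. The interviewer telephones, waits two days, telephones again and waits two more days. An email then goes out and, in parallel, "the Clinical Interviewer will contact Riverside staff involved in the study". The stated purpose is "to inquire about the participant's whereabouts in case information about changes in the participant's programmatic status" has not already reached the research team.

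**Who knows allocation.** Section 8 refers to "Peer specialists from Riverside who will be trained as Photovoice co-leaders". Section 7 says that the peers delivering Photovoice at a given site and wave also co-lead the single control session. Section 22 says that neither participants nor treatment providers are blinded. The recruitment text adds: "The Project Coordinator will contact each participant and explain their randomization condition".

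**Related form.** The Demographic Questionnaire in Section 7 covers "use of different mental health services in the past 3 months". An abbreviated form, limited to time-varying items, is used after baseline. Its items are not listed.

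**The concern.** Assessor blinding is the only blinding in this trial, and the sponsor chose to have it. The tracing step puts the blinded person in direct conversation, about a named participant, with agency staff who may know that participant's arm. Nothing in the procedure limits whom the interviewer may approach or what may be said in reply.

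What is at stake is the independence of scores that depend on the interviewer's judgement. Two measures in Section 7 are of that kind: the 21-item Quality of Life Scale, described as a rating from a semi-structured interview, and the 24-item BPRS. Community functioning is listed among the primary outcomes in Section 7, and the Quality of Life Scale may be its measure. Any unblinding by this route would fall on participants who are hard to reach, not on a random subset. An interviewer who learns the arm before post-treatment also still knows it at the 3- and 6-month visits.

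**Working it through.** The plan states no figure on this point, so the check sets the provisions side by side.

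1. **Is it the same person?** Yes. The interviewer who must be blind is the one named in the tracing step. The role is in the singular almost throughout; Section 9 once uses the plural.
2. **Can the people contacted know the arm?** They can. The group is defined only by involvement in the study. Riverside peer specialists trained as co-leaders fit that description, and because the same peers run the control session they can know the membership of both arms. The protocol does not say that they are the ones contacted.
3. **When would it happen?** Two waits of two days give 2 + 2 = 4 days after the first call, so the staff contact falls about 14 − 4 = 10 days before the due date. If the post-treatment visit is due near the end of the 10-week program (an assumption; the due date is not given), classes would still be running. At the 3- and 6-month visits they have ended, so a reply is less likely to mention them.
4. **Is there a safeguard?** None is described: no separate tracing role, no script for staff, no request to withhold the arm, no log of unblinding. All assessments are audiotaped, but the 10–15% check is for reliability and rater drift. Blinded re-rating is not described.
5. **Which outcomes are exposed?** The SAP names the Internalized Stigma scale, the Stigma Scale, the proactive coping subscales (Hypothesis 1) and the Temple participation scale (Hypothesis 2). From their descriptions in Section 7 all appear to be answered by the participant. The Quality of Life Scale and the BPRS are rated by the interviewer.
6. **The service-use items.** If they are repeated at post-treatment, a look-back of 3 months (about 13 weeks) covers all 10 weeks of the program. At 3 months it covers roughly the period after the program; at 6 months it does not reach back to it.

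**Illustration of size; every input is assumed.** For an interviewer-rated scale, let bias = share traced × share of contacts that disclose the arm × between-arm rating shift once unblinded.

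- Low: 0.10 × 0.25 × 0.2 SD = 0.005 SD.
- Middle: 0.30 × 0.50 × 0.3 SD = 0.045 SD.
- High: 0.30 × 1.00 × 0.5 SD = 0.15 SD.

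With 96 per arm, the standard error of a difference is √(2/96) = 0.144 SD. At an assumed two-sided 5% level, with no true effect, dropout or clustering, a bias of 0.045 SD gives a false-positive rate of about 6%, and 0.15 SD about 18%. The difference detectable with 80% power is (1.96 + 0.84) × 0.144 = 0.40 SD.

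**The case against.** The strongest reply is that the step is narrow. It applies only to non-responders, asks only about whereabouts and status, and speaks of contact with staff whose identity is not defined. Elsewhere the protocol describes Riverside staff as helping with referral and recruitment. Mention of a peer leader or a stigma session would not in itself identify the arm, since the same peers serve both. Traced participants who are never reached yield no rating at that visit. All of this stands. It makes disclosure incidental and conditional, but it does not close the route, because staff who know the allocation are not excluded.

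A reader might infer that the interviewer's blinding is the only protection against assessment bias for the whole trial, so that the primary tests are in danger. The documents do not support that. Participants know their arm and appear to supply the SAP-named outcomes themselves, so a perfect interviewer blind could not remove self-report bias. The SAP text names neither the Quality of Life Scale nor the BPRS.

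A reader might also infer that the interview itself unblinds, by asking about services at follow-up. Service use is plainly time-varying, so the items are probably repeated. But the abbreviated form is not itemised, its place in the interview is not given, and nothing says that Photovoice would be reported as a mental health service. This supports a conditional precaution only.

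Finally, the recruitment text reports 12 waves already recruited, so a change helps only the assessments that remain. That also stands.

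**Conclusion.** The point holds as a gap in how the blind is protected. The protocol requires a blind interviewer and gives that interviewer a contact that can incidentally disclose the arm, with no provision to prevent it. The exposure is most plausible before the post-treatment visit and matters mainly for the interviewer-rated scales. For the outcomes named in the SAP it amounts to possible influence during administration.

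The documents do not show that any unblinding occurred, and they give no means of sizing it. The range of 0.005 to 0.15 SD rests wholly on assumed inputs, its upper end needs every worst case at once, and it concerns rated scales only. It should not be read as an estimate of bias in the stigma, coping or participation results. The case for acting is that the correction is cheap and protects the trial's only blinding.

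**What to change.** - In the Section 7 contact procedure, assign the contact with agency staff to the Project Coordinator, who already knows allocation. The coordinator passes back to the interviewer only contact details and availability.
- Have the interviewer log any accidental unblinding at each remaining follow-up, and report it with the results. For assessments already done, report any unblinding that is known and state the limitation.
- Check the abbreviated questionnaire. If it repeats the 3-month service-use items, make sure that they come after the interviewer-rated scales.
- Leave the safety contact rules unchanged.

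**Cost.** Slightly slower tracing and a few more contacts for the coordinator; no new staff. If the service-use items have to be moved, the order of administration will differ between earlier and later visits, which should be recorded. The benefit is confined to assessments still to be done.

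### Protocol section 22: the stated duties to tell the PI cover unexpected SAEs, while the PI must report any SAE, and the written-report deadline has no clear starting point

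*Protocol*

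**What the plan says.** All the reporting rules stand in Protocol section 22 (Adverse Events). The section opens by tying adverse events to MA DMH guidelines and promising to follow the reporting guidelines. Their content is not given.

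**Into the PI.** Riverside staff are asked to "report any unexpected serious adverse event among study participants to the PI within 3 days of becoming aware". The next sentence reads: "The Project Coordinator will be required to report such events to the PI within 24 hours of becoming aware of their occurrence". *Such events* refers back to the unexpected SAEs just named.

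**Out from the PI.**
- DSMB and IRB: "The PI will follow the requirements of the Data Safety and Monitoring Board and the MA DMH IRB". For an SAE, with no qualifier as to expectedness or relatedness, this means "verbal notification as soon as possible and in writing by the next business day following the event".
- Funder: "The PI will notify NIMH within 7 days of becoming aware of the occurrence of a study-related serious adverse event".
- DSMB Chair, in the paragraph on the DSMB: the Chair "will be notified by the PI of serious adverse events that are study related using the protocol specified in the next paragraph".

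**Record.** "An ongoing record of all adverse events will be kept by the PI for use and review of the DSMB at the meetings".

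The SAP does not deal with safety reporting.

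**The concern.** These rules form one chain: the PI can pass on or record only what reaches the PI. The first link is worded more narrowly than the links that depend on it. *Unexpected* is not defined in the documents, so whoever sees the event at the agency has to judge expectedness before the PI sees it.

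There are two lesser problems. The reporting paragraph applies DSMB requirements to any SAE, while the DSMB paragraph limits notice to the Chair to study-related ones. And the staff, coordinator and NIMH time limits all run from awareness, whereas the written report to the DSMB and IRB is dated from the event, which may or may not be meant literally.

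At stake is whether the PI, and through the PI the IRB and DSMB, hears in time of every SAE that the protocol's own clause covers. No efficacy result depends on it.

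**Working it through.** The plan gives no figure to reproduce here. The check is a comparison of scopes, followed by a day count.

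**Scope.** Split SAEs by expectedness and by relation to the study, which gives 2 × 2 = 4 types.

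| Step (Protocol section 22) | Unexpected, related | Unexpected, unrelated | Expected, related | Expected, unrelated | Types covered |
|---|---|---|---|---|---|
| Staff and coordinator to PI | yes | yes | not stated | not stated | 2 of 4 |
| PI to DSMB and IRB | yes | yes | yes | yes | 4 of 4 |
| PI to NIMH | yes | no | yes | no | 2 of 4 |
| PI to DSMB Chair | yes | no | yes | no | 2 of 4 |
| PI's record | yes | yes | yes | yes | 4 of 4 |

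The two expected types have no stated inflow. One of them, expected and study-related, is owed to the IRB, NIMH and the DSMB Chair alike. For the two unrelated types, the second and fourth rows disagree on prompt DSMB notice. These are counts of categories, not of events. The documents give no SAE rate, so no number of missed reports can be derived.

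**Do other sections fill the gap?** Section 7 (retention procedures) has the interviewer ask Riverside about a participant who has not answered calls. Section 7 (data management) sets up a database that can track adverse events. Section 9 sends suicide-risk reports to Riverside clinical staff. None of these sets a duty or a time limit for telling the PI.

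**Timing, on the literal event clock.** Inputs from section 22 are the 3 days (staff), the 24 hours (coordinator) and the next-business-day deadline. Assumptions are no holidays, an awareness lag L of 0, 1 or 2 days, and a report to the PI k days after awareness. News that arrives on the due date counts as in time.

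- Days from event to due date, d: 1 for Monday to Thursday and Sunday, 3 for Friday, 2 for Saturday.
- The PI first hears too late if L + k > d.

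Staff with L = 0 and k = 3: 3 > 1 on Monday to Thursday and Sunday (2 days late), 3 > 2 on Saturday (1 day late), and 3 = 3 on Friday (in time). That is 6 of 7 event weekdays.

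| Awareness lag | k = 1 | k = 2 | k = 3 |
|---|---|---|---|
| L = 0 | 0 of 7 | 5 of 7 | 6 of 7 |
| L = 1 | 5 of 7 | 6 of 7 | 7 of 7 |

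If the 3 days are business days, L = 0 gives 7 of 7. The coordinator's 24 hours (k = 1) give 0 of 7 at L = 0, 5 of 7 at L = 1 and 6 of 7 at L = 2. These counts show which event days can go wrong; they are not an expected rate of late reports.

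**Timing, on an awareness clock.** If the deadline starts when the PI learns of the event, the staff interval has ended before the deadline begins to run. There is then no conflict for any weekday or lag.

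**The case against.** Four stronger readings are tempting, and the documents support none of them.

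*Staff are told to withhold expected SAEs.* The text names unexpected SAEs but does not say that only these are to be reported, and it does not tell staff to filter. The narrower scope follows from the absence of any other stated route.

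*SAEs will go unreported.* The MA DMH guidelines that section 22 invokes are not available here and might set a wider scope. Section 7 also suggests that other news may come in: the interviewer asks Riverside where information on a status change ("hospitalization, expulsion, etc.) has not been already provided to the research staff"), which presupposes that it sometimes has been. Section 22 promises continuous safety monitoring by the PI. So what can be shown is a gap in the stated rules, not a gap in practice. Even so, nothing in the protocol text itself puts a wider duty on Riverside staff or the coordinator.

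*The DSMB never sees unrelated SAEs.* It reviews the record of all adverse events at its meetings. The disagreement is only about which SAEs need prompt notice.

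*Written reports will be late.* That needs a literal event clock. A PI cannot report an event not yet known, so loose wording is a natural explanation. Verbal notice has no fixed date and is not in conflict with the staff interval. What stands is that the clause departs from the awareness wording used for the other three clocks and leaves its start open.

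It is also fair to say that the protocol describes a low-risk intervention. That bears on how often the gap would matter, not on whether the passages agree.

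**Conclusion.** The point holds in a limited form and should be corrected. The SAE scope stated for reports to the PI (2 of 4 types) is narrower than the scope that the PI must report to the DSMB and IRB and must record (4 of 4). This rests on the protocol text alone and could be narrowed by the MA DMH guidelines. The difference on prompt DSMB notice is real but softened by the meeting review. The timing point is conditional: up to 6 of 7 event weekdays with same-day awareness, full use of 3 calendar days and an event clock; none with an awareness clock. The DSMB and IRB requirements that would settle the clock are not in the documents.

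The reference to a next paragraph in the DSMB passage leads, in the text as given, to the list of attachments. That is an editorial slip and no more.

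**What to change.** Amend section 22 in three places.

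1. Reconcile the scopes so that the SAEs which Riverside staff and the coordinator report to the PI are at least as wide as those the PI must report and record. The PI, not the agency staff, then filters by recipient.
2. State whether the written-report clock starts at the event or at PI awareness. Make the staff interval compatible with that start and with the DSMB and IRB requirements, and say whether it counts calendar or business days.
3. State which SAEs need prompt DSMB notice, so that the reporting paragraph and the DSMB paragraph agree.

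Correct the paragraph pointer at the same time. The cost is a short amendment, a revised instruction to Riverside staff and slightly more reports for the PI to log. Sample size and analysis do not change.
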